8.3 Phase II Primary Endpoint – Progression-free Survival

The primary study hypothesis is that treatment with FLT3 ligand, CD40 agonist antibody, and SBRT (Arm 1) will improve progression-free survival (PFS) compared to standard therapy (Arm 2). Based on published data for patients with advanced NSCLC who require treatment after several lines of standard therapy, we expect that the median PFS duration for subjects on Arm 2 will be 5 months. Based on our recent study using FLT3 ligand and SBRT and the expectation that CD40 agonist antibody will enhance treatment efficacy, we hypothesize that the median PFS duration for subjects on Arm 1 will be 10 months. This improvement is approximately equivalent to a hazard reduction of 50%. We are employing a *randomized phase II screening design*, using $\alpha = 0.20$ (wherein a p-value <0.20 indicates a positive trial). We anticipate that study accrual will take place over 24 months, and we will analyze treatment efficacy 12 months after accrual is completed. We do not expect any subjects to be lost to follow-up before the primary endpoint occurs. Based on these assumptions, our total sample size of 46 subjects yields study power of 81% using a two-sided log-rank test.

We will compare the distributions of PFS between treatment arms using a two-sided log-rank test. The rates at various timepoints (e.g., every 6 months after randomization) and median PFS durations for each arm will be estimated using the Kaplan-Meier method. Associated 95% confidence intervals (CI) will be calculated using Greenwood's formula. Cox proportional hazards models will be used to estimate the impact of study therapy on PFS duration.

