2.3 Stereotactic Body Radiotherapy (SBRT)

In recent years, hypofractionated stereotactic body radiotherapy (SBRT) has emerged as an effective treatment option for numerous malignancies. SBRT uses the principles of intracranial stereotactic radiosurgery (large daily doses delivered precisely to a small target volume over a short treatment course) to treat extracranial disease sites. For stage I NSCLC, SBRT yields excellent local control rates²³⁻²⁵ and has now been proven to prolong survival compared to standard radiotherapy²⁶. Serious adverse

events following SBRT for lung tumors are very rare²⁷, except when aggressive SBRT regimens are used to treat central lesions²⁸. Importantly, highly-conformal delivery of SBRT allows relatively safe treatment of lung tumors in patients with poor pulmonary function²⁹. Similarly, SBRT yields low toxicity rates when employed to treat extrathoracic disease sites, such as the liver, skeleton, and adrenal gland³⁰⁻³³.

A wide variety of dosing and fractionation schedules has been used to deliver lung SBRT for NSCLC^{24,25,34,35}. Although there is evidence of a dose-response relationship when relatively low-dose regimens (BED < 100 Gy) are used,^{24,25} more intense regimens have yielded consistently excellent results and are considered to be ablative. These include 10-12.5 Gy x 4-5 fractions, 18-20 Gy x 3 fractions, and 25-34 Gy in a single fraction. The National Comprehensive Cancer Network (NCCN) provides guidelines for the selection of an SBRT (also known as SABR) schedule as well as relevant constraints for normal tissues, which will be adopted for this trial.

[figure not shown]
Several recent randomized trials suggest that, for patients with advanced NSCLC and limited (“oligometastatic”) disease, radical treatment with SBRT to all active sites of disease could delay disease progression and prolong overall survival^{32,36-38}. This principal is being tested for patients with oligometastatic NSCLC after first-line systemic therapy in NRG-LU002.

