2.7 SBRT for NSCLC Patients with Limited Disease Burden

Several phase II randomized trials have recently demonstrated that, for patients with “oligometastatic” and non-progressive NSCLC after first-line systemic therapy, comprehensive local therapy may delay disease progression and death³⁶⁻³⁸. This hypothesis is now being tested in a large multi-institutional trial (NCT03137771). Radical local therapy has also shown promise in other settings of limited metastatic disease^{32,73,74}. For advanced/metastatic NSCLC, current NCCN guidelines indicate that “definitive local therapy to isolated or limited metastatic sites... is an appropriate option in such cases if it can be delivered safely to the involved sites⁷⁵. ”

[figure not shown]
For patients in our practice who have limited (typically less than 3-5) sites of active disease after several lines of systemic therapy (leaving few appealing systemic treatment options), we routinely offer “comprehensive” SBRT as standard of care. As a result, *all subjects enrolled on this study for whom the treating physicians deem comprehensive SBRT to be safe and feasible will receive comprehensive SBRT*.

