3.0 PATIENT ELIGIBILITY

3.1 Inclusion Criteria

- Histologically proven NSCLC, not classically deemed to be amenable to curative therapy based on disease extent at the time of diagnosis or disease progression after the initial diagnosis

[figure not shown]
- Age \geq 18 years
- Prior treatment with at least two lines of systemic therapy for advanced NSCLC, including one line of platinum-based combination chemotherapy
 - Treatment with concurrent chemotherapy and immunotherapy can count as two lines of therapy for the purposes of study eligibility.
- Radiological assessments, including CT within 21 days prior to study entry and PET/CT within 42 days prior to study entry, demonstrating measurable disease that includes at least one pulmonary or extrapulmonary lesion \geq 1 cm in greatest dimension that would be amenable to SBRT and at least one measurable lesion that would be outside of the SBRT treatment fields
- ECOG performance status 0-2
- Both men and women enrolled in this trial must agree to use adequate birth control measures during the trial and for at least 90 days after last receipt of study therapy. Patients and/or partners who are surgically sterile or postmenopausal are exempt from this requirement.
- The following laboratory results, within 21 days prior to study registration:
 - Hemoglobin \geq 9.0 g/dL
 - Absolute neutrophil count \geq 1.5 \times 10⁹/L
 - Platelet count \geq 100 \times 10⁹/L
 - Serum creatinine \leq 1.5 \times ULN OR creatinine clearance (by Cockcroft-Gault formula) $>$ 60 mL/min
 - AST and ALT \leq 2.5 \times ULN
 - Total bilirubin \leq 2.0 \times ULN (except patients with Gilbert's syndrome, who must have a total bilirubin \leq 3.0 mg/dL)
 - Negative SARS-CoV-2 (COVID-19) PCR test
 - COVID-19 testing may be repeated periodically based on institutional policies and must be repeated for any subject with unexplained signs (e.g., imaging findings, fever) or symptoms (e.g., anosmia) concerning for COVID-19 infection or with recent known exposure to COVID-19.

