4.1 General Design

This is a randomized, open-label phase I/II study. Subjects will be randomized in a 1:1 ratio to receive FLT3 ligand, anti-CD40 antibody, and SBRT (Arm 1) versus standard care (Arm 2). Subjects on either study arm with limited disease will receive SBRT to all evident sites of active disease. Subjects on Arm 1 with extensive disease will initially receive SBRT to a single site of disease but may receive additional “cycles” of FLT3 ligand, anti-CD40 antibody, and SBRT at later time points. Subjects on Arm 2 with extensive disease are expected to receive some form of standard systemic therapy (e.g., docetaxel). Subjects on Arm 2 with limited disease may also receive standard systemic therapy following completion of SBRT to all sites of evident disease, at the discretion of the treating physicians. All subjects will be followed closely for treatment-related toxicities. Whole-body PET/CT and CT imaging will be performed prior to study entry, and restaging CT will be performed every 8 weeks thereafter.

In the phase I component of this study, subjects will be randomized between study arms until 6 subjects have been randomized to Arm 1. Study accrual will then be halted until 8 weeks after the last study subject begins treatment.

If the pre-specified safety criteria are achieved in the Phase I portion of this study, the study will proceed to phase II. The total sample size (Phase I and Phase II) will be 46 subjects. All 46 subjects will be included in efficacy analyses.

If the pre-specified safety criteria are not achieved in the Phase I portion of this study, the investigators and Celldex will review safety data from this trial as well as other trials using CDX-301 and CDX-1140 and determine if the experimental treatment regimen should be altered (e.g., by reducing the CDX-1140 dose). The study protocol would be amended accordingly, and Phase I component with the new treatment regimen would be added.

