8.0 STATISTICAL CONSIDERATIONS

8.1 Randomization Procedure

At the time of study registration, subjects will be stratified by EGFR/ALK mutation status and disease burden and then will be randomized 1:1 between the two study arms using a modified permuted block treatment allocation scheme¹¹⁵. Block sizes of 2 (65%) and 4 (35%) will be considered. Study subjects and study personnel will NOT be blinded with respect to the randomization result.

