8.4 Secondary Endpoints and Exploratory Analyses

Overall survival (OS) rates and median OS durations will be estimated using the Kaplan-Meier method. Exploratory comparisons of OS distributions between study arms will be performed using a two-sided log-rank test and Cox proportional hazards models.

Radiographic response rates will be characterized using descriptive statistics. The clinical benefit rate (CBR) will be defined as the percentage of subjects who achieve best response of confirmed CR or PR, or stable disease (SD) for at least four months. CBR in Arm 1 and Arm 2 will be compared using chi-square testing or Fisher

exact test, as appropriate. Objective response rate (ORR) will be defined as the percentage of subjects who do not receive comprehensive SBRT who achieve best response of confirmed CR or PR. ORR in Arm 1 and Arm 2 will be compared using chi-square testing or Fisher exact test, as appropriate.

Quality-of life (QoL) will be assessed using the EORTC QLQ-C30 and EORTC QLQ-LC13. Summary statistics (mean, standard deviation, median, 25th and 75th percentiles, and range) and the mean change from baseline of linear-transformed scores will be reported for all the items and subscales of the EORTC QLQ-C30 questionnaire and the QLQ-LC13, according to the EORTC scoring manual guidelines and the. Completion and compliance rates will be summarized at each timepoint by treatment arm. Only patients with a non-missing baseline assessment and at least one non-missing post-baseline assessment will be included in the analyses.

Daily step count averages at baseline and at various timepoints after study registration will be characterized using descriptive statistics. To test the hypothesis that study therapy preserves physical function compared to standard therapy, a linear mixed effects model with random coefficients using a restricted maximum likelihood procedure will be used to model daily step count as a function of study arm, using adjustment variables such as age and gender.

Exploratory multivariable and subgroup analyses of PFS and OS predictors will be performed. Adjustment/grouping variables will include baseline disease burden, performance status, NSCLC subtype, and prior response to immunotherapy.

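### Section 8.3 names no strata for the primary PFS log-rank test or Cox model, although randomisation is stratified by disease burden; naming burden is a cheap improvement with a small, conditional gain

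*Combined protocol and SAP*

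**What the plan says.** Section 8.1 states that "subjects will be stratified by EGFR/ALK mutation status and disease burden and then will be randomized 1:1 between the two study arms", which gives four cells, with permuted blocks of 2 (65%) and 4 (35%).

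For the primary endpoint, Section 8.3 states "We will compare the distributions of PFS between treatment arms using a two-sided log-rank test" and "Cox proportional hazards models will be used to estimate the impact of study therapy on PFS duration". It names no stratum or covariate for either. The test is two-sided, and p < 0.20 makes the trial positive. The section claims 81% power with 46 subjects.

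Burden enters the efficacy analysis of PFS only in Section 8.4, among exploratory multivariable and subgroup analyses: "Adjustment/grouping variables will include baseline disease burden, performance status, NSCLC subtype, and prior response to immunotherapy". Nothing in the documents says that the primary test is stratified.

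Burden also determines treatment. Section 4.1 states "Subjects on either study arm with limited disease will receive SBRT to all evident sites of active disease".

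**The concern.** When randomisation is balanced within a prognostic factor, chance imbalance in that factor can no longer add to the difference between arms. An unstratified log-rank test still uses a variance that allows for such imbalance. Its actual size therefore falls below nominal and some power is lost. Separately, pooling groups with different hazards pulls the marginal hazard ratio toward 1, even when the treatment effect is the same in each group.

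There is some reason to expect burden to be prognostic here, because it decides whether all active sites are irradiated. Section 2.3 says of patients with limited disease that "radical treatment with SBRT to all active sites of disease could delay disease progression and prolong overall survival".

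A second issue does not depend on that expectation. Section 8.3 refers to Cox models in the plural without listing terms, and Section 8.4 offers four candidate adjusters. In an open-label trial, which hazard ratio is the study estimate should be fixed in advance.

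**Working it through.** **Inputs from Sections 8.1 and 8.3.** 46 subjects, 1:1; blocks of 2 (65%) and 4 (35%) within four strata; control median 5 months, experimental 10 months (HR 0.50); uniform accrual over 24 months, analysis 12 months later; no loss to follow-up; two-sided alpha 0.20.

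**Step 1: the plan's own figure.** With exponential PFS, hazard λ = ln 2 / median, accrual A = 24 and further follow-up F = 12, the event probability is

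1 − [exp(−λF) − exp(−λ(A+F))] / (λA).

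- Median 5: 1 − (0.1895 − 0.0068)/3.327 = 0.945
- Median 10: 1 − (0.4353 − 0.0825)/1.664 = 0.788
- Expected events: 23 × (0.945 + 0.788) = 39.9

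Schoenfeld power: Φ(√(39.9/4) × ln 2 − 1.282) = Φ(2.19 − 1.28) = 81.8%. Simulation of a homogeneous population gives 81.0-81.2%. The stated 81% reproduces.

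**Step 2: simulation with burden as a prognostic factor.** These inputs are assumptions, because the documents do not give them:

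- limited-disease share 5-50%
- burden HR (limited v extensive) from 1.0 to 0.30
- treatment HR 0.50 within each stratum
- exponential PFS within strata, with the overall control median held at 5 months (at a 10% share: extensive v limited medians of 4.7 v 9.4 months for burden HR 0.50, and 4.6 v 13.1 for 0.35)
- 15% EGFR/ALK positive, not prognostic.

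There were 140,000 trials per setting for the three tables, with a Monte Carlo standard error of about 0.1 points for power. Changes were computed before rounding.

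Power (%) at nominal 0.20, unstratified v burden-stratified (change in points):

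| Burden HR | 5% limited | 10% limited | 20-50% limited |
|---|---|---|---|
| 1.0 | 81.1 v 80.3 (−0.7) | 81.1 v 80.1 (−1.0) | 81.1-81.2 v 79.7-80.0 (−1.1 to −1.4) |
| 0.50 | 80.1 v 80.5 (+0.4) | 79.4 v 80.1 (+0.7) | 76.9-78.3 v 79.2-79.9 (+1.6 to +2.3) |
| 0.35 | 79.3 v 80.5 (+1.2) | 77.5 v 80.0 (+2.4) | 71.5-74.9 v 78.3-79.5 (+4.6 to +6.9) |

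Actual size of the unstratified test at nominal 0.20:

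| Burden HR | 5% | 10% | 20-50% |
|---|---|---|---|
| 1.0 | 0.209-0.211 | 0.209-0.211 | 0.209-0.211 |
| 0.50 | 0.206 | 0.203 | 0.188-0.193 |
| 0.35 | 0.201 | 0.190 | 0.164-0.176 |

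The burden-stratified test stays at 0.208-0.212 in these settings.

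**Step 3: separate size from efficiency.** Each test is given its own critical value, the 80th percentile of |Z| under the null, so that both have actual size 0.20. Change in power from stratifying (points):

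| Burden HR | 5% | 10% | 20-50% |
|---|---|---|---|
| 1.0 | −0.7 | −1.0 | −1.1 to −1.3 |
| 0.50 | 0.0 | +0.1 | +0.2 to +0.5 |
| 0.35 | +0.5 | +0.6 | +1.4 to +2.5 |

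Most of the nominal gain is therefore restored size. At burden HR 0.30 the gains are 1.7 / 3.3 / 6.2-9.2 points nominal and 0.7 / 1.1 / 1.9-3.6 calibrated. At burden HR 0.70-0.85 (30,000-40,000 trials per setting) stratifying loses 0.3-1.1 points nominal and 0.4-1.3 calibrated.

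**Step 4: the hazard ratio (true value 0.50; 30,000-40,000 trials per setting).** The median unstratified Cox estimate is 0.49-0.51 at burden HR 0.70-1.0. It is 0.50 / 0.51 / 0.52 at burden HR 0.50 and 0.51 / 0.52 / 0.54-0.55 at 0.35, for limited shares of 5% / 10% / 20-50%. The burden-stratified Cox estimate is 0.49-0.50 throughout.

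**Step 5: all four cells.** A log-rank test stratified on burden and EGFR/ALK together loses 1.9-3.1 points when burden is not prognostic, against 0.7-1.4 for burden alone.

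**The case against.** An unstratified log-rank test after stratified randomisation is valid, and Section 8.3 specifies its sidedness, alpha and power assumptions. Choosing a stratified test instead is a choice between valid methods, and no error has been shown. This stands.

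The benefit rests on two unknowns, and parts of the documents point to the less favourable settings. The randomised evidence in Section 2.7 concerns disease described as "and non-progressive NSCLC after first-line systemic therapy, comprehensive local therapy may delay disease progression and death", whereas Section 3.1 requires "Prior treatment with at least two lines of systemic therapy for advanced NSCLC". Section 3.1 also requires a measurable lesion outside the SBRT fields; read literally, that leaves few subjects whose every active site is treated. Section 5.1.1 leaves the limited category to the treating physician's judgement, which may weaken its prognostic value. These points stand: they keep the expected gain small, and at a share of 10% or less the test choice matters little unless the burden effect is strong.

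Section 8.4 does plan burden-adjusted PFS analyses, but as exploratory ones. They do not settle the primary test or the reported hazard ratio.

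Finally, the proposal uses one of the two randomisation factors. That is a power judgement for 46 subjects, and it assumes that EGFR/ALK status is uncommon and not prognostic.

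**Conclusion.** The concern holds as an inexpensive improvement, not as a validity error. The gain depends on a clearly prognostic burden factor, and becomes material only with a strong effect (burden HR around 0.35 or lower) and a limited share of roughly 20% or more. Around a burden HR of 0.50 it is at most 2.3 points at the nominal level and 0.5 points after calibration. With a weak or absent burden effect there is a loss of at most 1.4 points. The exact figures rest on exponential PFS, a common treatment HR of 0.50 and the assumed shares and burden effects. The need to say which Cox model supplies the reported hazard ratio holds regardless of those assumptions.

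**What to change.** In Section 8.3:

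- Stratify the primary two-sided log-rank test by disease burden alone (limited v extensive), using the category recorded at randomisation.
- Take the reported hazard ratio from one named Cox model, stratified by or adjusted for burden.
- Report the unstratified log-rank test as a sensitivity analysis.
- Do not stratify the test on all four cells.

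The cost is two sentences plus a small edit to the power statement: under the plan's homogeneous assumption the burden-stratified test has 79.7-80.3% power rather than 81%. Randomisation, data collection and sample size do not change. If the sponsor expects limited disease in about 10% of subjects or fewer, or prefers the unstratified test, Section 8.3 should still state the choice and name the Cox model.

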8.4 Secondary Endpoints and Exploratory Analyses

Overall survival (OS) rates and median OS durations will be estimated using the Kaplan-Meier method. Exploratory comparisons of OS distributions between study arms will be performed using a two-sided log-rank test and Cox proportional hazards models.

Radiographic response rates will be characterized using descriptive statistics. The clinical benefit rate (CBR) will be defined as the percentage of subjects who achieve best response of confirmed CR or PR, or stable disease (SD) for at least four months. CBR in Arm 1 and Arm 2 will be compared using chi-square testing or Fisher

exact test, as appropriate. Objective response rate (ORR) will be defined as the percentage of subjects who do not receive comprehensive SBRT who achieve best response of confirmed CR or PR. ORR in Arm 1 and Arm 2 will be compared using chi-square testing or Fisher exact test, as appropriate.

Quality-of life (QoL) will be assessed using the EORTC QLQ-C30 and EORTC QLQ-LC13. Summary statistics (mean, standard deviation, median, 25th and 75th percentiles, and range) and the mean change from baseline of linear-transformed scores will be reported for all the items and subscales of the EORTC QLQ-C30 questionnaire and the QLQ-LC13, according to the EORTC scoring manual guidelines and the. Completion and compliance rates will be summarized at each timepoint by treatment arm. Only patients with a non-missing baseline assessment and at least one non-missing post-baseline assessment will be included in the analyses.

Daily step count averages at baseline and at various timepoints after study registration will be characterized using descriptive statistics. To test the hypothesis that study therapy preserves physical function compared to standard therapy, a linear mixed effects model with random coefficients using a restricted maximum likelihood procedure will be used to model daily step count as a function of study arm, using adjustment variables such as age and gender.

Exploratory multivariable and subgroup analyses of PFS and OS predictors will be performed. Adjustment/grouping variables will include baseline disease burden, performance status, NSCLC subtype, and prior response to immunotherapy.

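### Clinical benefit rate is tested without the disease-burden stratum used at randomisation, which costs some power if burden predicts benefit

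*Combined protocol and SAP*

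**What the plan says.** Section 8.1 states that "subjects will be stratified by EGFR/ALK mutation status and disease burden and then will be randomized 1:1 between the two study arms". On block sizes it adds: "Block sizes of 2 (65%) and 4 (35%) will be considered".

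Sections 4.1, 5.1.1 and 6.0 tie burden to treatment. Subjects with limited disease, on either arm, receive SBRT to every evident active site. Subjects with extensive disease do not.

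Section 8.4 defines CBR as the "percentage of subjects who achieve best response of confirmed CR or PR, or stable disease (SD) for at least four months" and then states "CBR in Arm 1 and Arm 2 will be compared using chi-square testing", or Fisher's exact test where that suits the data better. It names no stratified or adjusted version. The same section restricts ORR to subjects not given comprehensive SBRT, but places no such limit on CBR. Burden appears as an adjustment or grouping variable only for exploratory PFS and OS analyses.

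No alpha, power or expected rate is stated for CBR. The only criterion, "wherein a p-value <0.20 indicates a positive trial", is given in section 8.3 for PFS.

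**The concern.** Stable disease for four months counts as clinical benefit, so CBR depends on how long progression is delayed. Section 2.7 says comprehensive local therapy may delay progression in limited disease. It is therefore plausible that CBR differs between limited and extensive disease in both arms.

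Stratified allocation keeps the arms nearly balanced on burden, so differences between strata add almost nothing to the chance variation of the arm comparison. The pooled two-by-two test still counts those differences in its variance. If burden is prognostic, the p-value is then too large. At stake is the ability of a secondary comparison, with about 23 subjects per arm, to show a difference that exists.

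**Working it through.** **The plan's own figure.** The only power figure is for PFS: "our total sample size of 46 subjects yields study power of 81% using a two-sided log-rank test". With medians of 5 and 10 months, 24 months of uniform accrual and 12 months of further follow-up, the event probability is 1 − [exp(−12λ) − exp(−36λ)]/(24λ), where λ = ln 2/median. This gives 0.788 (Arm 1) and 0.945 (Arm 2), so 23 × (0.788 + 0.945) ≈ 39.9 events. Schoenfeld power at two-sided 0.20 is Φ(√(39.9/4) × ln 2 − 1.282) ≈ 82%, and simulation gives 81.3%. The figure reproduces. It says nothing about CBR, for which there is no figure to reproduce.

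**Inputs for CBR.**
- From the documents: 46 subjects at 1:1 (taken as 23 per arm), stratification by burden, pooled chi-square or Fisher.
- Assumed: 12 limited and 11 extensive subjects per arm (varied below), CBR by stratum, two-sided 5%.

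**Formulas.**
- Pooled chi-square: z = (p₁ − p₂)/√[2p̄(1 − p̄)/23], where p₁ and p₂ are the observed CBR in each arm and p̄ is the pooled rate.
- CMH without correction: [Σ(aₖ − mₖ/2)]²/ΣVₖ, with Vₖ = mₖ(2nₖ − mₖ)/[4(2nₖ − 1)]. Here nₖ is subjects per arm in stratum k, mₖ is all benefits in it and aₖ is those in Arm 1.
- Approximate size of the pooled test: 2Φ(−1.96/√R), where R is the mean within-stratum variance divided by the pooled variance.

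**Worked case, 70% limited and 30% extensive in both arms.** Within-stratum variance is 0.7 × 0.3 = 0.21. The pooled rate is (12 × 0.7 + 11 × 0.3)/23 = 0.509, with variance 0.250. So R = 0.84 and the approximate size is 2Φ(−2.14) = 3.2%. Exact enumeration gives 3.5%.

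**Exact results at nominal two-sided 5%.** Power uses an odds ratio of 3 in each stratum, with the listed rates in Arm 2. For 70/30, the Arm 1 odds are 3 × 0.7/0.3 = 7 and 3 × 0.3/0.7 = 1.286, that is 87.5% and 56.25%.

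| CBR limited/extensive | Gap (points) | Size: chi-square v CMH | Power: chi-square v CMH |
|---|---|---|---|
| 50/50 | 0 | 5.4% v 5.4% | 42% v 42% |
| 60/40 | 20 | 4.9% v 5.1% | 40% v 41% |
| 70/30 | 40 | 3.5% v 5.0% | 31% v 37% |
| 85/30 | 55 | 1.9% v 5.1% | – |
| 80/20 | 60 | 1.6% v 5.3% | 18% v 31% |

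**Sensitivity.**
- With 6 to 15 limited subjects of 23 per arm, chi-square size is 4.5% to 5.4% for gaps of 0 to 20 points, 3.1% to 4.0% at 40 and 1.6% to 1.8% at 60.
- Simulating the four-stratum block scheme, with 15% EGFR/ALK positive assumed, gives chi-square sizes of 5.0% (60/40), 3.7% to 3.8% (70/30) and 2.0% to 2.1% (80/20).
- At nominal 0.20, chi-square v CMH size is 18.6% v 18.5%, 17.6% v 18.4%, 14.7% v 19.7% and 9.6% v 20.4% at gaps of 0, 20, 40 and 60 points.

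**Which stratified test.** Three scenarios, 12 and 11 per arm, 5% level. A: no effect, 85/30. B: limited 95% v 80%, extensive 65% v 30%. C: limited 95% v 85%, extensive 55% v 20%.

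| Test | A (size) | B (power) | C (power) |
|---|---|---|---|
| Pooled chi-square | 1.9% | 42% | 30% |
| CMH, uncorrected | 5.1% | 52% | 47% |
| CMH, mid-p exact | 3.7% | 49% | 43% |
| CMH, fully exact conditional | 2.3% | 39% | 34% |
| CMH, continuity-corrected | 1.8% | 37% | 31% |

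**The case against.** A reader might infer that the planned test is far too conservative. The documents do not support that. It needs a CBR gap between strata of roughly 55 to 60 points, and they give no CBR by burden at all. Up to 20 points the loss is negligible, and at 40 points it is moderate.

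The low figures for Fisher's test could also mislead. Its size is 2.6% even when burden has no effect, because of discreteness at 23 per arm, so much of its conservatism has nothing to do with stratification. With average expected cell counts of about 7 or more in scenarios A to C, chi-square would normally be the test used.

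The 5% level is also an assumption. At 0.20, in scenario B, chi-square power is 74% and CMH 78%, a gap of only 4 points.

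Finally, a stratified test helps only in the right version. The fully exact conditional and continuity-corrected forms give back most of the gain and fall below chi-square in scenario B.

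All of this stands, and it limits the size of the point and the choice of remedy. It does not remove the point: the randomisation uses burden, the CBR test does not, and the uncorrected CMH test matches chi-square when burden is irrelevant and gains when it matters.

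**Conclusion.** The point holds as a minor one. If disease burden predicts CBR, the planned comparison is conservative and loses power: about 1 point at a 20-point gap, 6 at 40 points and 13 at 60 points, for an odds ratio of 3 at two-sided 5%. If burden does not predict CBR, nothing is lost.

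These sizes rest on assumed stratum rates, an assumed limited-disease share and an assumed alpha. The direction needs only that burden is prognostic and that the arms are balanced on it.

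Ignoring the stratum does not inflate false positives. CBR drives no decision rule, and the primary PFS conclusion is unaffected. The uncorrected CMH test is itself approximate: over gaps of 0 to 80 points its size is 4.5% to 5.4% at nominal 5%.

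**What to change.** In section 8.4, replace the CBR test with a Cochran-Mantel-Haenszel test stratified by disease burden only, without continuity correction, or with its mid-p exact version if the tables are sparse. Report the burden-stratified risk difference with its confidence interval. State the choice before any CBR data are compared by arm. Do not specify the fully exact conditional or continuity-corrected form.

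The cost is one sentence. Burden is already recorded for randomisation, and no change to sample size, data collection or conduct is needed.
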